14.2 Consideration of gene and mutation specific response rates

It is possible that certain combinations of mutation - primary cancer site will not respond to Everolimus therapy. Though the distribution of histologic subtypes among patients to be enrolled is unknown at this time, it is of interest to conduct exploratory analyses within these subgroups (for example, among patients with bladder cancer, PEComas, squamous cell lung cancer, etc.) Among a subgroup of 10 patients of any particular histology, there is 0.98 probability of observing at least 1 response among them, assuming an underlying response rate of 30%. Therefore, if 10 patients with TSC1/TSC2 mutations and a single cancer site are enrolled and no responses are observed among them, consideration may be given to halting enrollment of patients with cancers arising in that specific site. Since this lack of response may vary according to the primary site of cancer, in that instance we will continue to enroll patients TSC1/TSC2 mutations and different primary cancer sites.

14.3 Sample Size/Accrual Rate

We have a planned sample size of 30 patients, with either inactivating TSC1 or TSC2 mutations, or activating MTOR mutations, so it is estimated that this protocol will complete accrual in 48 months, making for an overall accrual rate of approximately 1.25 patients per month. We will be identifying patients for this study from the Oncopanel cancer genotyping at DFCI/BWH, the Impact cancer genotyping panel at MSKCC, and CLIA certified genotyping laboratories both at other DF/HCC institutions and external sites.

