3. PARTICIPANT SELECTION

This study will enroll 30 patients with inactivating mutations in TSC1 or TSC2, or activating mTOR mutations.

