14.1 Study Design/Endpoints

The primary objective of this trial is objective response rate according to RECIST 1.1 criteria.

Secondary objectives include duration of response, progression-free and overall survival. Duration of response is defined as the time from RECIST-confirmed response (CR+PR) to documented disease progression. Progression-free survival is defined as the time from study registration to documented disease progression per RECIST 1.1 or death from any cause, whichever occurs first. Patients not experiencing a PFS event will be censored at the date of their last disease assessment. Overall survival is defined as time from registration to death from any cause, censoring patients thought to be alive at the time of final analysis at the last date of follow up. We will also estimate toxicity via CTCAE version 4.0, and the association of IHC and whole exome sequencing results with patient outcomes and other genetic events.

We will estimate event-time distributions using the Kaplan-Meier method, using Greenwood's formula to estimate the variance and provide 90% confidence intervals for the medians, 6-month, and 1-year estimates. Categorical outcomes, such as toxicity and response, will be estimated and their corresponding 90% exact binomial confidence intervals will be provided.

For the cohort of patients with TSC1 and TSC2 mutations, we will conduct this study using a Simon's two-stage design. In the first stage we will enroll 21 patients and if a total of at least 4 responses (CR + PR) are observed among them, accrual to the second stage will open. If 3 or fewer responses are observed among the first 21 patients, the study will terminate. In the second stage, an additional 29 patients will be enrolled for a total study accrual of 50 patients. After accrual to the second stage is completed, we will declare study success if at least 8 responses are observed among the 50 registered patients. This design has a probability of stopping early after the first stage of accrual of 85% if the drug is ineffective; the overall power of the study to detect the targeted response rate of 30% (compared to a null of 10%) is 91% while controlling the type I error at a one-sided level of 0.07.

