For the cohort of 10 patients harboring mTOR mutations, we are somewhat limited in the inferences that can be made, however we would consider observing at least 2 responses in this cohort worthy of additional study. The maximum half-width of the 90% exact binomial confidence interval will be 23.5%.

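### Sections 3 and 14.3 plan 30 patients in total, while Section 14.1 specifies up to 50 TSC1/TSC2 patients plus 10 MTOR patients, and no available text says which is current

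*Combined protocol and SAP*

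**What the plan says.** Two sections give one total for all three genes together. Section 3: "This study will enroll 30 patients with inactivating mutations in TSC1 or TSC2, or activating mTOR mutations". Section 14.3: "We have a planned sample size of 30 patients, with either inactivating TSC1 or TSC2 mutations, or activating MTOR mutations". Section 14.3 then gives 48 months to complete accrual, "making for an overall accrual rate of approximately 1.25 patients per month".

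Section 14.1 describes a larger trial. For the TSC1/TSC2 cohort alone it sets a Simon two-stage design:

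- Stage 1: "In the first stage we will enroll 21 patients and if a total of at least 4 responses" are seen, the second stage opens; with 3 or fewer the study ends.
- Stage 2: "In the second stage, an additional 29 patients will be enrolled for a total study accrual of 50 patients".
- Final rule: "we will declare study success if at least 8 responses are observed among the 50 registered patients".
- Operating characteristics: early stopping of 85% if the drug is ineffective, a one-sided type I error of 0.07, and "the overall power of the study to detect the targeted response rate of 30% (compared to a null of 10%) is 91" per cent.

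Section 14.1 then adds a separate group, with its own informal threshold of 2 responses: "For the cohort of 10 patients harboring mTOR mutations".

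**The concern.** The total, the accrual rate, the primary decision rule and the power cannot all be true together. Objective response is the primary endpoint, and its only success criterion is a count out of 50 TSC1/TSC2 patients. If 30 is the operative total, a cohort that passes stage 1 has no written rule for declaring success, and the quoted type I error and power describe a different trial. A cut-off chosen after responses are known would not have controlled error rates. Sites and the IRB also need a single enrolment ceiling.

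**Working it through.** **1. Head count**

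Inputs are the stage sizes 21 and 29 and the MTOR cohort of 10 (Section 14.1), and the total of 30 (Sections 3 and 14.3).

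- Full accrual: 21 + 29 + 10 = 60.
- Stop after stage 1, MTOR cohort filled: 21 + 10 = 31.
- If 10 of the 30 are MTOR patients (an assumption; no split is given): 30 − 10 = 20 TSC1/TSC2 patients, one short of the first stage.

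**2. Accrual (Section 14.3)**

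- 48 months × 1.25 per month = 60.
- 30 ÷ 48 = 0.625 per month.
- 30 ÷ 1.25 = 24 months.

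The accrual figures agree with 60 and miss 30 by a factor of two.

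**3. The plan's own operating characteristics**

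Let X1 be the responses among the first 21 and X2 those among the next n2, both binomial with response rate p (null 0.10, target 0.30). For a final cut-off r:

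- Early stopping = P(X1 ≤ 3).
- P(success) = Σ over x from 4 to 21 of P(X1 = x) × P(X2 ≥ r − x).

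With n2 = 29 and r = 8:

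| Quantity | Exact | Stated |
|---|---|---|
| Early stopping, p = 0.10 | 0.848 | 85% |
| Type I error, p = 0.10 | 0.0662 | 0.07 |
| Power, p = 0.30 | 0.9125 | 91% |

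The stated figures reproduce at 50 TSC1/TSC2 patients. The early-stopping figure depends only on the first stage, so it does not discriminate between totals.

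**4. Same first stage, 30 TSC1/TSC2 patients**

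Keep 4 or more of 21, set n2 = 9, and vary the final cut-off:

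| Final cut-off of 30 | Type I error | Power |
|---|---|---|
| 4 | 0.152 | 0.914 |
| 5 | 0.113 | 0.910 |
| 6 | 0.060 | 0.886 |
| 7 | 0.024 | 0.822 |

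The first stage alone limits power to 1 − P(X1 ≤ 3 at p = 0.30) = 1 − 0.0856 = 0.914. Any final cut-off strict enough to bring type I error down to 0.07 takes power below 0.91. A search over 21 to 30 TSC1/TSC2 patients and final cut-offs 4 to 12 found no pair that gives both stated figures. The highest power with type I error at or below 0.07 is 0.886, at 6 or more of 30.

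**5. Other first stages, 30 TSC1/TSC2 patients**

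These are arithmetic examples only; none is in the protocol.

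| Rule | Early stopping under null | Type I error | Power |
|---|---|---|---|
| ≥3 of 20, then ≥6 of 30 | 0.677 | 0.0691 | 0.9126 |
| ≥5 of 27, then ≥6 of 30 | 0.873 | 0.0686 | 0.9146 |

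A trial of 30 TSC1/TSC2 patients can therefore reach about the stated error rates, but only with a different first stage: one that stops less often, or one that looks when 27 of 30 are already enrolled.

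**The case against.** The strongest reply is that 50 is not a fixed requirement. The second 29 patients enrol only after at least 4 responses in the first 21, and under the null the cohort stops at 21 with probability 0.848. Expected TSC1/TSC2 enrolment under the null is 21 + 29 × (1 − 0.848) = 25.4. On that view, 30 might be a forecast of typical accrual. The conditional nature of the 50 stands, so 60 is a maximum. The reply does not remove the conflict: stopping after stage 1 still gives 31 with the MTOR cohort, both sections present 30 as the planned enrolment rather than an expectation, and the accrual rate is built on 60.

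Three stronger readings should be resisted.

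- A reader might infer that a total of 30 forces a loss of power. That is so only if the first stage stays at 4 or more of 21. Step 5 shows that about 91% can be recovered when all 30 are TSC1/TSC2, at a cost in early stopping.
- A reader might infer that a 30-patient trial would have no usable rule at all. The stage 1 futility rule still works if at least 21 patients are TSC1/TSC2. What is missing is a success rule after stage 1 is passed.
- A reader might apply the cut-off of 8 to 30 or fewer patients and report the resulting power. No section proposes that rule, so the figure would not describe a defect in the written plan.

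**Conclusion.** The contradiction is real and must be resolved. Sections 3 and 14.3 plan 30 patients; Section 14.1 needs between 31 and 60, depending on stage 1, with the MTOR cohort filled. The stated operating characteristics belong to a maximum of 50 TSC1/TSC2 patients. With the written first stage and at most 30 such patients, power is at most 0.886 at the 0.07 level.

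The calculations assume exact binomial responses with the protocol's rates of 10% and 30%. The case in which the first stage cannot be filled rests on the further assumption that 10 of the 30 are MTOR patients. The accrual arithmetic fits 60, but that does not establish that 60 is intended; the 30 could equally be a later figure that was not carried through Section 14. The available text does not say, and it does not give enrolment or response status.

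**What to change.** Reconcile Sections 3, 14.1 and 14.3 by an IRB-approved amendment, as Section 13.1 requires, before the primary analysis. State the TSC1/TSC2 and MTOR cohort sizes explicitly, and say that the second-stage 29 are conditional on stage 1.

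- **If 60 is intended:** correct the two entries of 30. The decision rule, error rates and accrual rate then agree as written. The cost is an amendment that doubles the stated enrolment.
- **If 30 is intended:** restate the TSC1/TSC2 decision rule, early-stopping probability, type I error, power and accrual rate for the number of TSC1/TSC2 patients planned. Accrual becomes 0.625 per month over 48 months, or 24 months at 1.25 per month. Keeping 4 or more of 21 and the 0.07 level caps power at about 89% with 30 TSC1/TSC2 patients. If all 30 are TSC1/TSC2, a changed first stage can recover about 91%, at the cost of weaker early stopping (68% with 3 or more of 20) or a later interim look (27 of 30). With fewer than 30 TSC1/TSC2 patients, every figure must be recomputed.

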15. PUBLICATION PLAN

The results will be made public within 12 months of the end of the last patient's last visit. The initial release of data will be in a peer-reviewed journal or in an abstract that meets the requirements of the International Committee of Medical Journal Editors. A full report of outcomes will be made public no later than three years after the end of data collection.

17. APPENDICES

Appendix A: Performance Status Criteria

ECOG Performance Status Scale		Karnofsky Performance Scale	
Grade	Description	Percent	Description
0	Normal activity. Fully active, able to carry on all pre-disease performance without restriction.	100	Normal, no complaints, no evidence of disease.
		90	Able to carry on normal activity; minor signs or symptoms of disease.
1	Symptoms, but ambulatory. Restricted in physically strenuous activity, but ambulatory and able to carry out work of a light or sedentary nature (e.g., light housework, office work).	80	Normal activity with effort; some signs or symptoms of disease.
		70	Cares for self, unable to carry on normal activity or to do active work.
2	In bed < 50% of the time. Ambulatory and capable of all self-care, but unable to carry out any work activities. Up and about more than 50% of waking hours.	60	Requires occasional assistance, but is able to care for most of his/her needs.
		50	Requires considerable assistance and frequent medical care.
3	In bed >50% of the time. Capable of only limited self-care, confined to bed or chair more than 50% of waking hours.	40	Disabled, requires special care and assistance.
		30	Severely disabled, hospitalization indicated. Death not imminent.
4	100% bedridden. Completely disabled. Cannot carry on any self-care. Totally confined to bed or chair.	20	Very sick, hospitalization indicated. Death not imminent.
		10	Moribund, fatal processes progressing rapidly.
5	Dead.	0	Dead.

Appendix C: Data and Safety Monitoring Plan

DFCI IRB Protocol #: 14-229

1. INTRODUCTION

The Dana-Farber/Harvard Cancer Center Multi-Center Data and Safety Monitoring Plan (DF/HCC DSMP) outlines the procedures for conducting a DF/HCC Multi-Center research protocol. The DF/HCC DSMP should serve as a reference for any sites external to DF/HCC that will be participating in the research protocol.

1.1 Purpose

To establish standards that will ensure that a Dana-Farber/Harvard Cancer Center Multi-Center protocol will comply with Federal Regulations, Health Insurance Portability and Accountability Act (HIPAA) requirements and applicable DF/HCC Standard Operating Procedures.

1.2 Multi-Center Data and Safety Monitoring Plan Definitions

DF/HCC Multi-Center Protocol: A research protocol in which one or more outside institutions are collaborating with Dana-Farber/Harvard Cancer Center where a DF/HCC investigator is the sponsor. DF/HCC includes Dana-Farber/Partners Cancer Care (DF/PCC) Network Clinical Trial Affiliates.

Lead Institution: One of the Dana-Farber/Harvard Cancer Center consortium members (Dana-Farber Cancer Institute (DFCI), Massachusetts General Hospital (MGH), Beth Israel Deaconess Medical Center (BIDMC), Boston Children's Hospital (BCH), Brigham and Women's Hospital (BWH)) responsible for the coordination, development, submission, and approval of a protocol as well as its subsequent amendments per the DFCI IRB and applicable regulatory guidelines (Food and Drug Administration (FDA), etc.). The Lead Institution is typically the home of the DF/HCC Sponsor. The Lead Institution also typically serves as the Coordinating Center for the DF/HCC Multi-Center Protocol.

DF/HCC Sponsor: The person sponsoring the submitted Multi-Center protocol. Within DF/HCC, this person is the Overall Principal Investigator who takes responsibility for initiation, management and conduct of the protocol at all research locations. In applicable protocols, the DF/HCC Sponsor will serve as the single liaison with any regulatory agencies. The DF/HCC Sponsor has ultimate authority over the protocol and is responsible for the conduct of the study at DF/HCC and all Participating Institutions. In most cases the DF/HCC Sponsor is the same person as the DF/HCC Overall Principal Investigator; however, both roles can be filled by two different people.

Participating Institution: An institution that is outside the DF/HCC and DF/PCC consortium that is collaborating with DF/HCC on a protocol where the sponsor is a DF/HCC Investigator. The Participating Institution acknowledges the DF/HCC Sponsor as having the ultimate authority and responsibility for the overall conduct of the study.

Coordinating Center: The entity (i.e. Lead Institution, Medical Monitor, Contract Research Organization (CRO), etc) that provides administrative support to the DF/HCC

Sponsor in order that he/she may fulfill the responsibilities outlined in the protocol document and DSMP, and as specified in applicable regulatory guidelines (i.e. Multi-Center Guidelines). In general, the Lead Institution is the Coordinating Center for the DF/HCC Multi-Center Protocol. Should the DF/HCC Sponsor decide to use a CRO, the CRO will be deemed the Coordinating Center.

DF/HCC Quality Assurance Office for Clinical Trials: A group within DF/HCC responsible for registering human subjects for trials, ensuring high-quality standards are used for data collection and the ongoing management of clinical trials, auditing, and data and safety monitoring. ODQ also coordinates quality assurance efforts related to multi-center clinical research.

2. GENERAL ROLES AND RESPONSIBILITIES

For DF/HCC Multi-Center Protocols, the DF/HCC Sponsor, the Coordinating Center, and the Participating Institutions are expected to adhere to the following general responsibilities:

2.1 DF/HCC Sponsor

The DF/HCC Sponsor, [name], Ph.D. will accept responsibility for all aspects of conducting a DF/HCC Multi-Center protocol which includes but is not limited to:

- Oversee the coordination, development, submission, and approval of the protocol as well as subsequent amendments.
- Ensure that the investigators, study team members, and Participating Institutions are qualified and appropriately resourced to conduct the protocol.
- Include the Multi-Center Data and Safety Monitoring Plan as an appendix to the protocol.
- Ensure all Participating Institutions are using the correct version of the protocol.
- Ensure that each participating investigator and study team member receives adequate protocol training and/or a Site Initiation Visit prior to enrolling participants and throughout trial's conduct as needed.
- Ensure the protocol will be provided to each participating site in a language understandable to all applicable site personnel when English is not the primary language.
- Monitor progress and overall conduct of the study at all Participating Institutions.
- Ensure all DFCI Institutional Review Board (IRB), DF/HCC and other applicable reporting requirements are met.
- Review data and maintain timely submission of data for study analysis.
- Ensure compliance with all requirements as set forth in the Code of Federal Regulations, applicable DF/HCC requirements, HIPAA requirements, and the approved protocol.
- Commit to the provision that the protocol will not be rewritten or modified by anyone other than the DF/HCC Sponsor.
- Identify and qualify Participating Institutions and obtain accrual commitments prior to extending the protocol to that site.
- Monitor accrual and address Participating Institutions that are not meeting their accrual requirements.

2.2 Coordinating Center

The general responsibilities of the Coordinating Center may include but are not limited to:

- Assist in protocol development.
- Review registration materials for eligibility and register participants from Participating Institutions with DF/HCCODQ.
- Distribute protocol and informed consent document updates to Participating Institutions as needed.
- Oversee the data collection process from Participating Institutions.
- Maintain documentation of Serious Adverse Event (SAE) reports and deviations/violation submitted by Participating Institutions and provide to the DF/HCC Sponsor for timely review.
- Distribute serious adverse events reported to the DF/HCC Sponsor that fall under the DFCI IRB Adverse Event Reporting Policy to all Participating Institutions.
- Provide Participating Institutions with information regarding DF/HCC requirements that they will be expected to comply with.
- Carry out plan to monitor Participating Institutions either by on-site or remote monitoring.
- Maintain Regulatory documents of all Participating Institutions which includes but is not limited to the following: local IRB approvals/notifications from all Participating Institutions, confirmation of Federal Wide Assurances (FWAs) for all sites, all SAE submissions, Screening Logs for all sites, IRB approved consents for all sites
- Conduct regular communications with all Participating Institutions (conference calls, emails, etc) and maintain documentation all relevant communications.

2.3 Participating Institution

Each Participating Institution is expected to comply with all applicable federal regulations and DF/HCC requirements, the protocol and HIPAA requirements.

The general responsibilities for each Participating Institution may include but are not limited to:

- Document the delegation of research specific activities to study personnel.
- Commit to the accrual of participants to the protocol.
- Submit protocol and/or amendments to their local IRB.
- Maintain regulatory files as per sponsor requirements.
- Provide the Coordinating Center with regulatory documents or source documents as requested.
- Participate in protocol training prior to enrolling participants and throughout the trial as required (i.e. teleconferences).
- Update Coordinating Center with research staff changes on a timely basis.
- Register participants through the Coordinating Center prior to beginning research related activities.
- Submit Serious Adverse Event (SAE) reports to local IRB per local requirements and to the Coordinating Center, in accordance with DF/HCC requirements. Submit protocol deviations and violations to local IRB per local requirements and to the DF/HCC Sponsor in accordance with DF/HCC requirements.
- Order, store and dispense investigational agents and/or other protocol mandated drugs per federal guidelines and protocol requirements.
- Have office space, office equipment, and internet access that meet HIPAA standards.
- Participate in any quality assurance activities and meet with monitors or auditors at the conclusion of a visit to review findings.
- Promptly provide follow-up and/or corrective action plans for any monitoring queries or audit findings.

3. DF/HCC REQUIREMENTS FOR MULTI-CENTER PROTOCOLS

The following section will clarify DF/HCC Requirements and further detail the expectations for participating in a DF/HCC Multi-Center protocol.

3.1 Protocol Distribution

The Coordinating Center will distribute the final DFCI IRB approved protocol and any subsequent amended protocols to all Participating Institutions.

3.2 Protocol Revisions and Closures

The Participating Institutions will receive notification of protocol revisions and closures from the Coordinating Center. It is the individual Participating Institution's responsibility to notify its IRB of these revisions.

- **Non life-threatening revisions:** Participating Institutions will receive written notification of protocol revisions regarding non life-threatening events from the

Coordinating Center. Non-life-threatening protocol revisions must be IRB approved and implemented within 90 days from receipt of the notification.

- **Revisions for life-threatening causes:** Participating Institutions will receive immediate notification from the Coordinating Center concerning protocol revisions required to protect lives with follow-up by fax, mail, e-mail, etc. Life-threatening protocol revisions will be implemented immediately followed by IRB request for approval.
- **Protocol closures and temporary holds:** Participating Institutions will receive notification of protocol closures and temporary holds from the Coordinating Center. Closures and holds will be effective immediately. In addition, the Coordinating Center, will update the Participating Institutions on an ongoing basis about protocol accrual data so that they will be aware of imminent protocol closures.

